# Appendix A

|                                                                                                                                                                                                                                                                                                                            |                                                                                                                                                                                                                                                                                                                                                                                                                                                                   |  |  |
|----------------------------------------------------------------------------------------------------------------------------------------------------------------------------------------------------------------------------------------------------------------------------------------------------------------------------|-------------------------------------------------------------------------------------------------------------------------------------------------------------------------------------------------------------------------------------------------------------------------------------------------------------------------------------------------------------------------------------------------------------------------------------------------------------------|--|--|
| Hemoglobin <9 g/dL                                                                                                                                                                                                                                                                                                         | Measured 180 days prior to and including the day of drug initiation in any diagnosis position and in an inpatient or outpatient care setting

Anemia:
ICD-9 Dx:
282.x (hereditary hemolytic anemias)
283.x (acquired hemolytic anemias, autoimmune etc)
284.x (aplastic anemia and other bone marrow failure syndromes)                                                                                                                  |  |  |
| Serum creatinine >2.5 mg/dL (221 umol/L)                                                                                                                                                                                                                                                                                   | Measured 180 days prior to and including the day of drug initiation in any diagnosis position and in an inpatient or an outpatient care setting

CKD, ESRD:
ICD-9 Dx:
585.4x, 585.5x, 585.6x: CKD 4, 5, ESRD
586.xx: renal failure

ICD-10 Dx:
N19.xx
N18.4x Chronic kidney disease, stage 4 (severe)
N18.5x Chronic kidney disease, stage 5
N18.6x End stage renal disease
N18.9x Chronic kidney disease, unspecified |  |  |
| Calculated creatinine clearance <25 ml/min                                                                                                                                                                                                                                                                                 |                                                                                                                                                                                                                                                                                                                                                                                                                                                                   |  |  |
| ALT or AST >2 times upper limit of normal                                                                                                                                                                                                                                                                                  | N/A
(Incorporated into moderate/severe liver disease above)                                                                                                                                                                                                                                                                                                                                                                                                    |  |  |
| Total bilirubin >1.5 times upper limit of normal (unless an alternative causative factor is identified [eg, Gilbert's syndrome]).                                                                                                                                                                                          |                                                                                                                                                                                                                                                                                                                                                                                                                                                                   |  |  |
| Heparin-induced thrombocytopenia;                                                                                                                                                                                                                                                                                          | Measured 180 days prior to and including the day of drug initiation in any position and in an inpatient or outpatient care setting

Heparin induced thrombocytopenia (HIT)
ICD-9 Dx: 289.84
ICD-10 Dx: D75.82                                                                                                                                                                                                                                  |  |  |
| Allergic reaction to unfractionated heparin, LMWH, fondaparinux, or any VKA.                                                                                                                                                                                                                                               | N/A                                                                                                                                                                                                                                                                                                                                                                                                                                                               |  |  |
| DVT or PE treatment with more than two doses of fondaparinux or a LMWH that is labeled for once-daily dosing, or more than three doses of a LMWH that is labeled for twice-daily dosing, or continuous infusion of unfractionated heparin for more than 36 hours, before the first administration of study drug; and/or -- | N/A                                                                                                                                                                                                                                                                                                                                                                                                                                                               |  |  |
| DVT or PE treatment with more than two doses of oral VKA therapy before the first administration of study drug.                                                                                                                                                                                                            | N/A                                                                                                                                                                                                                                                                                                                                                                                                                                                               |  |  |
| Treatment with apixaban in a previous clinical trial.                                                                                                                                                                                                                                                                      | N/A                                                                                                                                                                                                                                                                                                                                                                                                                                                               |  |  |
| Subjects requiring aspirin (ASA) >165 mg/day at randomization.                                                                                                                                                                                                                                                             | Measured 1 day prior to and including the day of drug initiation in any diagnosis position and in an inpatient or outpatient care setting

Aspirin (prescription only)
dose greater than >165 mg                                                                                                                                                                                                                                                         |  |  |
| Subjects requiring dual antiplatelet therapy (ASA plus clopidogrel or ASA plus ticlopidine) at randomization. Subjects who transition from dual antiplatelet therapy to monotherapy prior to randomization will be eligible for the trial.                                                                                 | Measured 1 day prior to and including the day of drug initiation in any diagnosis position and in an inpatient or outpatient care setting
(both concurrent prescription and combination products)
Aspirin + clopidogrel
or
Aspirin + ticlopidine                                                                                                                                                                                                      |  |  |
| Prisoners or subjects who are involuntarily incarcerated                                                                                                                                                                                                                                                                   | N/A                                                                                                                                                                                                                                                                                                                                                                                                                                                               |  |  |
| Subjects who are compulsorily detained for treatment of either a psychiatric or physical (eg, infectious disease) illness                                                                                                                                                                                                  | N/A                                                                                                                                                                                                                                                                                                                                                                                                                                                               |  |  |
| Receiving concurrent investigational agents or has received an investigational agent within the past 30 days prior to the first dose of study treatment (with the exception of approved medications being used for an approved indication, eg, investigating a new dosing regimen for an approved indication)              | N/A                                                                                                                                                                                                                                                                                                                                                                                                                                                               |  |  |
| Any condition, which in the opinion of the investigator, would put the subject at an unacceptable risk from participating in the study                                                                                                                                                                                     | N/A                                                                                                                                                                                                                                                                                                                                                                                                                                                               |  |  |
| Any other medical, social, logistical, or psychological reason, which in the opinion of the investigator, would preclude compliance with, or successful completion of, the study protocol.                                                                                                                                 | N/A                                                                                                                                                                                                                                                                                                                                                                                                                                                               |  |  |

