| Excluded based on Exclusion # 15 - Uncontrolled Hypertension and based on Exclusion # 16 - thrombocytopenia                 | -26 | 4,297        | -36 | 6,369        | -78  | 8,539        |
| Excluded based on Exclusion # 17 – anemia, Exclusion # 18 - CKD/ESRD, and Exclusion # 22 - Heparin-induced thrombocytopenia | -33 | 4,264        | -31 | 6,338        | -139 | 8,400        |
| Excluded based on Exclusion # 27 - aspirin (ASA) >165 mg                                                                    | 0   | 4,264        | 0   | 6,338        | 0    | 8,400        |
| Excluded based on Exclusion # 28 - ASA plus clopidogrel or ASA plus ticlopidine                                             | 0   | 4,264        | 0   | 6,338        | 0    | 8,400        |
| Final cohort                                                                                                         |     | 4,264 |     | 6,338 |      | 8,400 |

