| Trial details- Secondary approval, Successful NI with label change                                                                                                                                                                                                                                                                                                                                                                                                                                   |                                                                                                                                                                                                                                                             |                                                                                                                                                                                                                                                                                  | ICD-10 codes are not listed in this document because of excel cell size limitations and excessive number of ICD-10 codes. Full ICD-10 code lists will be available in the above Google Drive Folder ( link above ). ICD-9 to ICD-10 code conversions were completed using a SAS macro that implements forward/backward mapping based on the CMS ICD-9 to ICD-10 mapping: https://www.ncbi.nlm.nih.gov/pmc/articles/PMC5300333/ |

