| ...Missing; n (%)                                                           | 1,305 (88.7%)   | 2,401 (86.3%)   | 0.07  | 2,453 (99.6%)         | 3,838 (99.1%)     | 0.06    | N/A         | N/A         | 3,758 (95.5%)    | 6,239 (93.7%)   | 0.08        |         |  |
| Lab result number- Hemoglobin mean (only >0 included)                       | 255             | 568             |       | 13                    | 41                |         | N/A         | N/A         | 268              | 609             |             |         |  |
| ...mean (sd)                                                                | 13.68 (1.85)    | 13.90 (1.82)    | -0.12 | 18,472.91 (45,243.58) | 14.22 (1.44)      | 0.58    | N/A         | N/A         | 909.09 (9627.75) | 13.92 (1.80)    | 0.13        |         |  |
| ...Missing; n (%)                                                           | 1,217 (82.7%)   | 2,215 (79.6%)   | 0.08  | 2,451 (99.5%)         | 3,833 (98.9%)     | 0.07    | N/A         | N/A         | 3,668 (93.2%)    | 6,048 (90.9%)   | 0.09        |         |  |
| Lab result number- Serum sodium mean (only >90 and <190 included)           | 283             | 641             |       | 16                    | 50                |         | N/A         | N/A         | 299              | 691             |             |         |  |
| ...mean (sd)                                                                | 140.35 (2.52)   | 140.27 (2.65)   | 0.03  | 138.74 (3.71)         | 139.42 (2.77)     | -0.21   | N/A         | N/A         | 140.26 (2.60)    | 140.21 (2.66)   | 0.02        |         |  |
| ...Missing; n (%)                                                           | 1,189 (80.8%)   | 2,142 (77.0%)   | 0.09  | 2,448 (99.4%)         | 3,824 (98.7%)     | 0.07    | N/A         | N/A         | 3,637 (92.4%)    | 5,966 (89.6%)   | 0.10        |         |  |
| Lab result number- Albumin mean (only >0 and <=10 included)                 | 254             | 602             |       | 14                    | 41                |         | N/A         | N/A         | 268              | 643             |             |         |  |
| ...mean (sd)                                                                | 4.05 (0.45)     | 4.16 (0.37)     | -0.27 | 4.10 (0.28)           | 4.09 (0.41)       | 0.03    | N/A         | N/A         | 4.05 (0.44)      | 4.16 (0.37)     | -0.27       |         |  |

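### The hemoglobin <9 g/dL exclusion is coded as hemolytic and aplastic anemia only, and balance on anemia cannot be seen in about 97% of the matched cohort

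*Combined protocol and SAP*

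**What the plan says.** In the exclusion criteria of Appendix A, the trial's "Hemoglobin <9 g/dL" is implemented through diagnosis codes in the 180 days up to and including drug initiation, in any position, inpatient or outpatient. The codes listed are:

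- "282.x (hereditary hemolytic anemias"
- "283.x (acquired hemolytic anemias, autoimmune etc"
- "284.x (aplastic anemia and other bone marrow failure syndromes"

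The row lists no ICD-10 codes. The header of Appendix A explains why: "ICD-10 codes are not listed in this document because of excel cell size limitations". It adds that "ICD-9 to ICD-10 code conversions were completed using a SAS macro". The absence of ICD-10 codes is therefore not an error, and the external lists would be expected to keep the same three disease groups.

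In the Section 5.3 flowchart the anemia exclusion is part of a combined step, "Excluded based on Exclusion # 17 – anemia, Exclusion # 18 - CKD/ESRD, and Exclusion # 22 - Heparin-induced thrombocytopenia", which removes 33, 31 and 139 patients in Optum, MarketScan and Medicare.

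Neither the unmatched nor the PS-matched table in Appendix B has an anemia diagnosis row. Both carry "Lab result number- Hemoglobin mean (only >0 included", which is N/A in Medicare. Section 9 says the propensity score takes the complete covariate list. It does not say whether the laboratory means are included, or how missing values are handled if they are.

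**The concern.** The trial criterion is a threshold that applies whatever the cause. The implementation is a list of causes that applies whatever the level. A patient with hemoglobin below 9 g/dL from blood loss or iron deficiency stays in, and a patient with a mild hereditary hemolytic disorder is removed. The creatinine criterion in the same appendix is handled differently: its codes include general categories such as unspecified renal failure and unspecified chronic kidney disease. The anemia row has no general category.

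A loose exclusion matters less if the propensity score adjusts for the same characteristic. Here nothing in the covariate tables does so for anemia as a diagnosis, and the hemoglobin row is nearly empty. Major bleeding is the assay-sensitivity endpoint (Section 1.5) and the safety outcome (Section 6.3.1). Baseline anemia is plausibly related to it. If warfarin and apixaban starters differed in baseline anemia after matching, the bleeding comparison would carry that difference and the planned balance table would not show it.

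**Working it through.** **1. Reproduce the plan's missingness figure.** The PS-matched table gives hemoglobin as missing for 1,782 (95.2%) warfarin and 1,757 (93.9%) apixaban patients in the pooled column. The denominator is Optum plus MarketScan, 490 + 1,381 = 1,871 per arm.

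- Warfarin: 1,782 / 1,871 = 95.2%
- Apixaban: 1,757 / 1,871 = 93.9%

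Both reproduce. The pooled percentages leave Medicare out, so they understate the gap.

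**2. Coverage over the whole matched cohort (7,140).**

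| Database | With a value (warfarin + apixaban) | Matched patients | Share |
|---|---|---|---|
| Optum | 83 + 97 = 180 | 980 | 18.4% |
| MarketScan | 6 + 17 = 23 | 2,762 | 0.8% |
| Medicare | 0 | 3,398 | 0% |
| All | 203 | 7,140 | 2.8% |

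No value exists for 7,140 − 203 = 6,937 patients (97.2%).

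**3. Quality of the values.** The matched MarketScan warfarin mean is 40,008.30 (SD 62,283.25) from 6 patients. The row's only filter is that the value exceeds zero. Only the Optum values can be used for a comparison between arms.

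**4. What the usable values show.** Matched Optum means (SD) are 13.73 (1.94) for warfarin and 13.73 (1.83) for apixaban, with a standardized difference of 0.00. Treating the two groups as independent samples, the standard error of the difference is √(1.94²/83 + 1.83²/97) = √(0.0453 + 0.0345) = 0.283. The 95% half-width is 1.96 × 0.283 = 0.55 g/dL. The means agree, but on 180 patients.

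**5. Share of tested patients below the threshold.** Assuming normality, P(Hb < 9) = Φ((9 − mean)/SD).

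- Warfarin: Φ((9 − 13.73)/1.94) = Φ(−2.44) = 0.7%
- Apixaban: Φ((9 − 13.73)/1.83) = Φ(−2.58) = 0.5%

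**6. The flowchart step.** Patients removed, over patients entering the step:

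- Optum: 33 / 4,297 = 0.77%
- MarketScan: 31 / 6,369 = 0.49%
- Medicare: 139 / 8,539 = 1.63%
- Total: 203 / 19,205 = 1.06% (the match with the 203 in step 2 is a coincidence)

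The step merges three criteria late in a sequence, so the number removed for anemia cannot be recovered. These counts are not evidence for or against leakage.

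**The case against.** The strongest reply is that the consequence is small and partly handled elsewhere. Most of this stands.

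- **Bleeding is addressed directly.** Appendix A excludes HAS-BLED of 3 or more, inpatient intracranial and gastrointestinal bleeding within 180 days, gross hematuria, and overt major bleeding. Appendix B carries gastrointestinal, urogenital and other bleeds and peptic ulcer disease. Where they can be computed, the matched standardized differences for these rows are at most 0.04 in absolute value. Matched HAS-BLED differences are −0.02, 0.00 and −0.01. This covers part of the pathway, but these rows record bleeding events and related disease, not anemia. The documents do not list the components of HAS-BLED or the comorbidity index, so neither can be shown to include anemia or to omit it.
- **The row may already be flagged as a proxy.** Appendix A has a colour key that grades how well each criterion can be measured in claims. The colours could not be read here, so this remains open.
- **The external ICD-10 list could be broader.** Mapping from the ICD-9 groups makes that unlikely, but it cannot be checked.

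A reader might infer from the unmatched Optum row (13.68 against 13.90, standardized difference −0.12) that anemia is imbalanced between arms and biases the bleeding result. The documents do not support that. The analysis is PS-matched, and the matched row shows equal means. A reader might also look at a milder cut-off, where more patients would fall. That does not bear on a criterion set at 9 g/dL.

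Applying the laboratory threshold in Optum as an exclusion is also tempting. Before matching, Φ((9 − 13.68)/1.85) = 0.57% and Φ((9 − 13.90)/1.82) = 0.35%. The rule would remove about 255 × 0.0057 + 568 × 0.0035 = 3.4 of 4,255 patients, and it would make eligibility depend on having been tested.

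**Conclusion.** The point holds, as a minor one. The listed codes do not measure low hemoglobin, no anemia diagnosis covariate appears in the tables, and the one laboratory row covers 2.8% of matched patients and none in Medicare, which supplies 3,398 of the 7,140. Balance on anemia is therefore unobserved for about 97% of the cohort.

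Where it can be seen, the effect is small: equal matched Optum means, and about 0.5% to 0.7% of tested patients below 9 g/dL. That estimate assumes normality. It speaks for the rest of the cohort only if tested Optum patients resemble everyone else, which the documents do not show in either direction. The finding is about a confounder that cannot be checked. It does not establish bias in the bleeding comparison. That anemia predicts bleeding is an assumption made here and is not stated in the plan.

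**What to change.** Before the outcome analysis (Section 13 is still blank):

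1. Add one covariate for coded anemia in the 180 days up to and including initiation, covering blood-loss, iron-deficiency, chronic-disease and unspecified anemia, to the propensity score in Optum, MarketScan and Medicare.
2. Report its frequency and standardized difference by arm, before and after matching, in Appendix B.
3. State in Appendix A that the hemoglobin criterion is only partly measurable in claims, and keep the existing codes as they are.
4. Use the Optum hemoglobin values at most in a sensitivity analysis, not as an exclusion.

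The cost is one code list and a rerun of the match, so the balance tables, and the Section 10 figures if the number of pairs changes, would need updating. The limitation is that a diagnosis code says little about severity, which is why the covariate belongs in adjustment and not in the eligibility rules.
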